3.5 Rationale for Dosage Regimen and Study Drug Dosage

To propose dosage for this study, we extensively reviewed the pharmacokinetics of simvastatin including bioavailability, hepatic metabolism, serum levels and tissue distribution (1, 11-13). We also used published epidemiologic, animal and in vitro fibroid studies (9, 10, 14). About 60-80% of orally administered simvastatin is absorbed, 5% is bioavailable, and 78-87% is metabolized by liver, including several active metabolites. With rodents metabolizing statins about 25 fold compared to humans (1), 20 µg/g body weight/day subcutaneously was effective in the animal study (10). In addition, in vitro data shows effective concentrations as low as 0.1 µM. Importantly, dosage range for simvastatin in hyperlipidemia at 10-80 mg/day orally is associated with a peak plasma level of approximately 0.1-0.3 µM, with many active metabolites extending efficacy beyond simvastatin plasma level. Thus, 40 mg/day orally in humans appears appropriate.

3.6 Known and Potential Risks

Potential risks are primarily those of simvastatin. We will counsel all study candidates about potential side effects of simvastatin as per NIH prescribing information (1). The most important ones are muscle side effects such as muscle pain, tenderness, weakness or the more serious rhabdomyolysis. Other side effects include gastrointestinal (GI) side effects, liver function abnormalities, allergic reactions, headache, confusion, memory problems, fever, joint pain, cold symptoms, skin rash and sleep problems. The full list of side effects will be discussed at length with potential study candidates and a printed handout will be given as well.

The study nurse will remain in contact with the study subject throughout the study duration and will monitor the subject for any side effects and adverse events that may occur.

4. SELECTION AND ENROLLMENT OF STUDY SUBJECTS

4.1 Inclusion Criteria

To be eligible, subjects must meet all of these criteria:

- 4.1.1 Signed informed written consent
- 4.1.2 Gender: female
- 4.1.3 Age: 18-55 years at time of signing consent
- 4.1.4 BMI of subjects: $< 45 \text{ kg/m}^2$
- 4.1.5 Uterine fibroids:
 - 4.1.5.1 Diagnosed by ultrasound (MRI will be used only if ultrasound is inconclusive)
 - 4.1.5.2 Number: any number of fibroids
 - 4.1.5.3 Location: submucosal or intramural
 - 4.1.5.4 At least one fibroid of diameter $> 3\text{cm}$
- 4.1.6 Symptoms: one or more of the following symptoms of Heavy menstrual bleeding (HMB), defined as:

Experienced cyclic (22 to 35 days) abnormal uterine bleeding (heavy or prolonged) in at least 3 of the last 6 menstrual periods, including menstrual bleeding lasting 5 or more days or heavy bleeding per participant recall. Examples of heavy bleeding may include, but are not limited to the following:

 - 4.1.6.1 Requires the use of double protection to manage menstrual bleeding

- 4.1.6.2 Menstrual bleeding accompanied by the sensation of “gushing” or “flooding”
- 4.1.6.3 Saturates more than 1 tampon or sanitary pad per hour for 3 or more consecutive hours
- 4.1.6.4 Regularly needs to change the tampon or sanitary pad at night or regularly soils bedclothes
- 4.1.6.5 Heavy bleeding that affects work, school, or social activities
- 4.1.6.6 Pelvic pain/ pressure likely caused by fibroids
- 4.1.7 Plan for surgery (hysterectomy or myomectomy)
- 4.1.8 Normal Pap smear within the last year
- 4.1.9 Use of contraception during study such as non-hormonal contraceptives, intrauterine devices (IUD)/ intrauterine systems (IUS), barrier contraceptives, abstinence or sterilization

4.2 Exclusion Criteria

To be eligible, subjects must not meet any of these criteria:

- 4.2.1 Pregnancy or lactation.
- 4.2.2 History or current uterine, cervical or ovarian cancer.
- 4.2.3 Current endometrial hyperplasia or history of atypical endometrial hyperplasia. Endometrial biopsy will be done during screening if not done within last 12 months.
- 4.2.4 Suspicion of leiomyosarcoma.
- 4.2.5 Recent rapid growth of fibroids (i.e. doubling in size within 1-6 months period).
- 4.2.6 Unevaluated gynecologic abnormalities (unexplained vaginal bleeding, cervical dysplasia, or abnormal adnexal/ovarian mass).
- 4.2.7 Menopausal status.
- 4.2.8 Surgery is urgently indicated (<3 months) for medical or social reasons.
- 4.2.9 Hemoglobin \leq 6 g/dL.
- 4.2.10 Currently enrolled in another investigational study.
- 4.2.11 Mental condition or other barrier preventing informed written consent. Allergy or hypersensitivity to simvastatin.
- 4.2.12 Current use of simvastatin or other drugs of the same class.
- 4.2.13 Concomitant administration of strong CYP3A4 inhibitors including itraconazole, ketoconazole, posaconazole, voriconazole, erythromycin, clarithromycin, elithromycin,

HIV protease inhibitors, boceprevir, telaprevir, nefazodone, and cobicistat-containing products.

- 4.2.14 Concomitant administration of gemfibrozil, cyclosporine, or danazol, verapamil, diltiazem, amiodarone, diltiazem, dronedarone, amlodipine, ranozoline, lopitamide, and grapefruit juice.
- 4.2.15 Active liver disease, which may include unexplained persistent elevations in hepatic transaminase levels.(elevation of AST and/or ALT > 2 s.d. above the normal range at screening visit)
- 4.2.16 Known increased risk or diagnosis of a myopathy.

4.3 Study Enrollment Procedures

Recruitment will occur through referrals from gynecologists and primary care physicians for diagnosis and treatment of leiomyoma. All recruitment materials such as flyers will be sent to the IRB for review prior to dissemination. The discussion for enrollment in this study will be deferred until the women, in consultation with their physician, have made the decision to undergo hysterectomy or myomectomy. The main goal of screening is to ascertain if a fibroid can be obtained for evaluation post-surgery.

NOTE: Women undergoing other operative approaches to hysterectomy or myomectomy will be considered to be a subject in the study if a fibroid can be obtained intact.

A screening / enrollment log will be kept for documenting the reasons for ineligibility and non-participation of the candidates in the study.

Prior to obtaining informed consent from the participants, the study investigator will provide subjects with adequate information about the study, including risks and benefits, and answer any questions. This will provide the opportunity for the participants to consider all available options and understand their rights as a subject. The investigator will ensure that the subject comprehends this information in order to agree to participate in the clinical trial.

The subject must sign a statement (complying with the requirements of the U.S. Code of Federal Regulations, Title 21 CFR Part 50) which indicates that they have given their consent to participate in the study.

A flow chart of the study design and study related procedures is depicted in Figure 1 and Table 1. All the study related visits and procedures will occur in an outpatient area at Johns Hopkins.

At the screening visit the following procedures will be performed:

1. Complete history including medical conditions, headaches, depression, and chest pain. Reproductive health history regarding sexually transmitted infections, gynecologic conditions, menstrual history, contraceptive use, pregnancy history and smoking/ alcohol consumption history.
2. Physical examination with pelvic exam.
3. Review of concomitant medications.
4. Pregnancy test (Urine beta-hCG).
5. Laboratory testing including: CBC with differential, hemoglobin, hematocrit, ferritin, liver enzymes and lipid panel. Total amount of blood <20 ml. Blood will be drawn and held for research purposes.
6. Evaluation of fibroid size (volume) and location by ultrasound and/or MRI (only if ultrasound is inconclusive) by study physicians.

After enrollment the following procedures will be performed:

1. Standardized questionnaires (all attached in the appendix) will be administered to assess:
 - Quality of life and sexual activity questionnaires. These instruments have been used to assess subject's response in treatment of fibroids and are accepted surveys. (Uterine Fibroid Symptom and Health-related Quality of Life Questionnaire (UFS-QOL) and Female Sexual Function Index (FSFI)).
 - Pain (McGill Pain Questionnaire (MPQ) and Visual Analog Scale (VAS)).
2. A baseline ultrasound scan of the uterus with careful measurement of fibroid size in three dimensions (width, height and depth, example 4 cm x 4 cm by 5 cm).

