Inclusion criteria	
To be eligible, subjects must meet all of these criteria:
 
 • Signed informed written consent. • Gender: female.

A double blinded, phase II, randomized controlled trial to study the effects of simvastatin in patients with uterine leiomyoma.

	
 • Age: 18-55 years at time of signing consent. • BMI of subjects: < 45 kg/m². • Uterine fibroids: 
 • Diagnosed by ultrasound (MRI will be used only if ultrasound is inconclusive). • Number: any number of fibroids. • Location: submucosal or intramural. • At least one fibroid of diameter > 3cm. • Symptoms: one or more of the following symptoms of heavy menstrual bleeding (HMB), defined as: Experienced cyclic (22 to 35 days) abnormal uterine bleeding (heavy or prolonged) in at least 3 of the last 6 menstrual periods, including menstrual bleeding lasting 5 or more days or heavy bleeding per participant recall. Examples of heavy bleeding may include, but are not limited to the following: 
 • Requires the use of double protection to manage menstrual bleeding. • Menstrual bleeding accompanied by the sensation of “gushing” or “flooding”. • Saturates more than 1 tampon or sanitary pad per hour for 3 or more consecutive hours. • Regularly needs to change the tampon or sanitary pad at night or regularly soils bedclothes. • Heavy bleeding that affects work, school, or social activities. • Pelvic pain/ pressure likely caused by fibroids. • Plan for surgery (hysterectomy or myomectomy). • Normal Pap smear within the last year. • Use of contraception during study such as non-hormonal oral contraceptives, intrauterine devices (IUD)/ intrauterine systems (IUS), barrier contraceptives, abstinence or sterilization.
Exclusion criteria	To be eligible, subjects must not meet any of these criteria:

A double blinded, phase II, randomized controlled trial to study the effects of simvastatin in patients with uterine leiomyoma.

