3.2 Sample Size Determination

We plan to enroll 60 study participants (30 in each arm). With a 20% anticipated withdrawal rate (from prior experience in similar studies), we plan to recruit 72 subjects. Sample size was estimated based on pre-clinical results of tissue effect where we expect a difference of 0.2 (20% effect size). This is a pilot study, and based on a 20% effect size and ability to measure within 0.5 centimeter (sigma) with an alpha of 0.5 and power of 0.8, the sample size is 50 subjects using a two sided t-test. We will enroll 60 subjects, to be conservative, which provides confidence that we will observe a difference, if one exists.

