The study medication will be dispensed through the Investigational Drug Pharmacy at Johns Hopkins. The subject will be informed about the medication intake. The study medication is an oral tablet to be taken once a day in the evening at the same time. The dose of the simvastatin group is 40 mg/ day.

The restricted foods such as grapefruit, cranberry juice, and dietary supplements will be discussed with the subject.

At one time the participant will be provided medication for 6 weeks. The study nurse will contact the participant every week at the participant’s preferred time to ensure compliance and monitor any adverse events that may occur after starting the intake of the medication.

Visit 3 and 4: At 6 and 12 weeks from Drug Initiation Visit

Visits 3, and 4 will be at 6 and 12 weeks after the initiation of the study drug. These will occur at Johns Hopkins outpatient clinic to follow up with the study participant at intervals throughout the study duration of 12 weeks.

There will be review of concomitant medications that the subject is taking and an adverse events assessment at each visit. The restricted foods such as grapefruit, cranberry juice, and dietary supplements will be discussed with the subject.

The study questionnaires will be filled at visit 4. The subject will be informed about the ultrasound result at 12 weeks, and counselled about the need for surgery if there are significant changes in fibroid size.

Follow up Visit

The participant will have their scheduled hysterectomy or myomectomy and the fibroid sample will be collected and evaluated for histologic effects of simvastatin on fibroids.

The standard clinical care follow up will be provided to the subject by their gynecologists.

The study team will follow up with the subjects after their surgery at their 2 and 6 weeks post-surgery visits to monitor for any adverse events. The subjects will fill the final questionnaires for the study at the 6 week post surgery visit.

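### No repeat readings of fibroid dimensions are required, although the stated 0.5 cm precision exceeds the per-dimension change from a 20% volume fall in fibroids under about 7 cm (if the 20% means volume)

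*Protocol*

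**What the plan says.** Fibroid size is the primary outcome (Protocol 6.3). The efficacy objective in 2.1.1 is tumor volume by ultrasound before and after treatment, and the screening list in 4.3 also equates size with volume. Table 1 schedules ultrasound at Visit 1 and Visit 4 only.

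- Measurement: after enrollment, 4.3 calls for a baseline scan with "careful measurement of fibroid size in three dimensions (width, height and depth, example 4 cm x 4 cm by 5 cm". It does not say how many readings are taken per dimension. No section describes how the Visit 4 measurement is made.
- Precision: 3.2 refers to an "ability to measure within 0.5 centimeter (sigma" without saying whether this applies to one dimension, a mean diameter or a change.
- Effect: in 3.2, "we expect a difference of 0.2 (20% effect size", with the basis given as "Sample size was estimated based on pre-clinical results of tissue effect". It does not say 20% of what.
- Entry size: "At least one fibroid of diameter > 3cm" (Synopsis and 4.1.5.4), with no upper limit.
- Use at Visit 4: under 6.2.1 the woman is told her ultrasound result and "counselled about the need for surgery if there are significant changes in fibroid size". Section 3.3 says the same. Neither gives a size for such a change or refers to the 0.5 cm.

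**The concern.** A volume built from three lengths carries the error of all three, and a change in volume carries it from two scans. If one reading is uncertain by 0.5 cm and the hoped-for shrinkage moves each dimension by less than that, much of the observed change in smaller fibroids is measurement noise. That widens the standard error of the primary comparison in a trial of 60 women. The same scan also feeds a conversation with the individual woman, where nothing averages out. Averaging repeat readings within the two scheduled scans would reduce part of this noise. It has to be specified before the scans are done, because an analysis plan cannot recover it afterwards.

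**Working it through.** **The plan's own figure.** Section 3.2 states that "the sample size is 50 subjects using a two sided t-test", "with an alpha of 0.5 and power of 0.8". With difference 0.2 and sigma 0.5, a two-sided two-sample test at the printed alpha needs 27 per arm (54) by the t distribution or 29 per arm (58) by the normal. At alpha 0.05 it needs 100 or 99 per arm. Only a one-sample or paired normal calculation at 0.05 gives 50. So the 50 does not reproduce as a two-arm comparison and does not show what sigma or 20% meant. That is a separate matter, and nothing below depends on it.

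**Step 1: shrinkage per dimension.** A 20% volume fall with unchanged shape shrinks each dimension by 1 − 0.8^(1/3) = 0.0717.

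- 3 cm: 0.22 cm
- 5 cm: 0.36 cm
- 4 x 4 x 5 cm: 0.29, 0.29 and 0.36 cm
- Diameter at which the change equals 0.5 cm: 0.5 / 0.0717 = 6.98 cm

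**Step 2: dependence on the undefined terms.** The threshold under other readings:

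| Reading of 20% and sigma | Threshold |
|---|---|
| Volume; sigma is the error of the mean of three independent dimensions, one scan (0.5/√3) | 4.0 cm |
| Volume; sigma as above, for the pre-post change (0.5·√(2/3)) | 5.7 cm |
| Volume; sigma is the error of one linear reading | 7.0 cm |
| Volume; pre-post difference of one diameter (0.5·√2) | 9.9 cm |
| Diameter; sigma is the error of one linear reading (0.5/0.2) | 2.5 cm |

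The last is below the 3 cm entry limit.

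**Step 3: error in the volume change.** Assume independent errors of SD 0.5 cm per dimension. The CV of one volume is √Σ(0.5/dᵢ)², and the SD of the log-volume change is √2 times that.

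- 3 cm: √2 × 0.289 = 0.41
- 4 x 4 x 5 cm: √2 × 0.203 = 0.29
- 5 cm: √2 × 0.173 = 0.25

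**Step 4: power.** Assumptions: effect −ln 0.8 = 0.223 on the log scale, true between-woman variation in change of SD 0.2 (not in the protocol), 30 per arm, two-sided 0.05, noncentral t. For 4 x 4 x 5 cm with single readings, total SD = √(0.287² + 0.2²) = 0.350, SE = 0.350·√(2/30) = 0.090, ratio 2.47, power 68%. With three averaged readings, the error variance is multiplied by b + (1 − b)/3, where b is the share of error variance arising between scans.

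| Fibroid | Single reading | Three, b = 0.5 | Three, b = 0 (best case) |
|---|---|---|---|
| 3 cm | 46% | 59% | 79% |
| 4 x 4 x 5 cm | 68% | 79% | 91% |
| 5 cm | 77% | 85% | 93% |

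At b = 1 the gain is nil.

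**Step 5: sensitivity to the assumed 0.2.** For 4 x 4 x 5 cm, in the same column order: 80%, 92% and 99% at a true SD of 0.1; 53%, 61% and 70% at 0.3; 41%, 45% and 50% at 0.4. If 0.5 cm is already the SD of the change per dimension, single readings give 85% at a true SD of 0.2.

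**The case against.** - **The 20% is not stated to be volume.** It is paired with a sigma in centimetres and drawn from pre-clinical tissue work. On a diameter reading every qualifying fibroid would change by more than 0.5 cm. This stands as a condition on the point. Volume is still the more natural reading, since 2.1.1 and 4.3 treat size as volume.
- **Silence on repeats is not a statement that one set is taken.** A reader might infer that each scan yields exactly one set of three dimensions. The protocol does not say so. Section 4.3 also lists a size evaluation at screening and, separately, a baseline scan after enrollment, while Table 1 shows ultrasound at Visit 1 and Visit 4 only. What can be said is that no repeat reading is required.
- **Reading technique belongs in an imaging manual.** This has some force. But the protocol already sets the measurement method in 4.3 and a precision in 3.2, so the place to tie the two together is here.
- **Sample size.** A reader might take 30 less 20%, or 24 per arm, as the analysed number. Section 3.2 recruits 72 to cover withdrawal (72 × 0.8 = 57.6, about 29 per arm) and 10.2 speaks of 60 evaluable women, so 24 overstates the deficit.
- **Counselling.** With independent errors, an unchanged 4 x 4 x 5 cm fibroid would appear to fall by 20% or more in about 22% of women. A reader might infer that those women would be counselled wrongly. The documents set no 20% trigger, and 8.2 ties surgery being unnecessary to symptom improvement, so that inference is not supported.
- **Bias.** In a blinded randomized comparison this error is non-differential. It costs precision and gives no ground for saying that the arm comparison is distorted.

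**Conclusion.** The point holds as a cheap improvement to the measurement method. It does not show that the primary analysis is invalid. Provided that 20% means volume and 0.5 cm is the error of one linear reading, the stated precision exceeds the expected per-dimension change in fibroids under about 7 cm, including the protocol's own example. On the other volume readings checked the threshold lies between 4.0 and 9.9 cm, always above the entry limit; on a diameter reading the conflict is gone. The likely benefit of three averaged readings in the 4 x 4 x 5 cm case, at 30 per arm and a true SD of 0.2, is a rise in power from about 68% to about 79% with an even split of error variance. It reaches 91% only if all the error is between readings, and approaches zero if nearly all of it is between scans. The protocol does not give that split. Confidence is moderate, because the protocol leaves both key terms undefined.

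**What to change.** 1. In 4.3 and 6.2, require each dimension of the measured fibroid to be read three times within the same examination at Visit 1 and at Visit 4, by the same method, and the readings averaged for the analysed volume. Report the repeat-reading SD with the primary result, which shows how much of the 0.5 cm was removable.
2. In 3.2, state whether the 20% refers to volume or diameter, and what sigma is the SD of: one reading, one volume or a change.
3. Reconcile the wording on changes in fibroid size in 3.3 and 6.2.1 with the precision stated in 3.2. No clinical threshold is proposed here.

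The cost is a few minutes per scan, with no added visit, scan or reader. Items 2 and 3 are text changes.

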5. STUDY INTERVENTIONS

5.1 Interventions, Administration, Duration

5.1.1 **Intervention:** Simvastatin tablets and placebo tablets will be encapsulated prior to being dispensed to the subject from the investigational drug pharmacy and will look similar. The participant will receive the study medication for a duration of 6 weeks at a time. The dose of the simvastatin tablets is 40 mg/ day. More information of dosage is in the section for “Rationale for Dosage Regimen”. The subject will be advised to take the medicine in the evening at a fixed time every day. The placebo will consist of Starch 1500 packed into matching capsules.

A safety report will be generated and will include updated information such as adverse event monitoring, compliance rates, etc. about all the participants in the study.

5.1.2 **Administration:** The study drug will be taken orally by the participant for a total period of 12 weeks divided into intervals of 6 weeks each followed by study visits with the team. The participants will be advised to take the tablet orally at the same time every day, in the evening, with water.

5.1.3 **Duration:** The participants will take the study drug/ placebo for a duration of 6 weeks at a time (12 weeks in total). The prescriptions for the study drug/ placebo will be refilled at an interval of 6 weeks. The subject will be seen at the drug intake initiation week (Visit 2), after 6 weeks (Visit 3) and 12 weeks (Visit 4). After the last visit, the subject will undergo their scheduled hysterectomy/ myomectomy to collect fibroid samples.

After the hysterectomy / myomectomy, fibroid samples collected will be examined and stored for further evaluations.

Thus, the participant will effectively be a part of the study for a duration of 12 weeks prior to their hysterectomy/ myomectomy. The study team will follow up the subjects after their surgery at their 2 and 6 weeks post-surgery visits to monitor for any adverse events.

5.2 Handling of the Study Interventions

Study medication is Simvastatin Tablets, USP.. The 40 mg tablets will be dispensed to the participants for this study. Both simvastatin and placebo will be encapsulated, prepared and dispensed by the Johns Hopkins Investigational Drug Service (IDS). A manual of operations describing procedures for storage and dispensation of the study drug/ placebo and accountability records will be kept at the IDS.

5.3 Concomitant Medications

No medication will be given outside of the study drug simvastatin or the placebo except for treatment of conditions that are clinically indicated. Prophylactic antibiotics may be given prior to hysterectomy or myomectomy based on standard pre-operative procedures at the research site.

Prescription or over-the-counter systemic medications will be allowed at the discretion of the investigators. Medicines will be allowed for depression, headache migraines, allergies, hypertension, and other medical conditions that are not part of the exclusion criteria.

All women will be protected from pregnancy by intrauterine devices (IUD)/ intrauterine systems (IUS), barrier contraceptives, abstinence or sterilization for the duration of the study.

All concomitant medication must be recorded in the subject's medical records. Additionally, any diagnostic, therapeutic, or surgical procedure performed during the study period will be recorded including the date, indication, and description of the procedure(s) and any clinical findings.

